**23. APPENDIX E: CLINICAL LABORATORY TESTS**

CLINICAL CHEMISTRY	HEMATOLOGY
The following clinical chemistry tests will be performed at the Screening Visit, at Postdosing Days 1, and at the Final Visit	The following hematology tests will be performed at the Screening Visit, at Postdosing Day 1, and at the Final Visit
Calcium	Hemoglobin
Chloride	Hematocrit
Creatinine	RBC count
Glucose	WBC count with differential
Alkaline phosphatase	Platelet count
Potassium	URINALYSIS
Sodium	The following urinalysis tests will be performed at the Screening Visit and the Final Visit
Aspartate aminotransferase (AST)	pH
Alanine aminotransferase (ALT)	Specific gravity
Blood urea nitrogen (BUN)	Glucose
Phosphorus	Protein
Protein total	RBC
Albumin	WBC
Bilirubin total	Ketones
LIPID PANEL	Bilirubin
Cholesterol	Nitrite
Triglycerides	Urobilinogen
LDL	Microscopic examination (performed on abnormal findings unless otherwise specified)
HDL	Macroscopic examination
SEROLOGY	
The following serology tests will be performed at the Screening Visit	
HIV antibody test	
HbsAg Hepatitis B test	
Hepatitis C (HCV) antibody test	The following test will be performed at Screening Visit and at Treatment Day -1
The following tests will be performed at the Screening Visit, at Treatment Days -1*, 8, 15, 22, 27** (Treatments "A", "B", and "D"), Treatment Day 29 (Treatments "C" and "D"), and at Post-Treatment Days 7, 14, 21. *Day - 1 for Treatments "A", "B" and "C", Day 1 for Treatment "D" ** Day 27 for Treatments "A" and "B" only	Serum pregnancy ( $\beta$ -hCG) test (Treatment "A", "B" and "C")
Urine drug screen test	The following test will be performed at

	Treatment Days 1* (*Treatment D) 15, 27** (**Treatments "A", and, "B"), Postdosing Day 1*** (**Treatment "C" and "D") and Postdosing Day 28 (Final Visit)
Urine cotinine test	Urine pregnancy test

Subject Number: \_\_\_\_\_ Subject initials: \_\_\_\_\_

***PART 2: 28-Day Post-Dosing Evaluation Period***

Date (MM/DD)																												
Post-dosing Day →	1	2	3	4	5	6	7	8	9	10	11	12	13	14	15	16	17	18	19	20	21	22	23	24	25	26	27	28
Bleeding Diary																												
Check if NO BLEEDING/SPOTTING																												
Check if SPOTTING																												
Check if LIGHT bleeding																												
Check if NORMAL bleeding																												
Check if HEAVY bleeding																												

Principal Investigator or Designee Signature: \_\_\_\_\_ Date: \_\_\_\_\_

**25. APPENDIX G: ACCEPTABLE DAYS FOR INITIATION OF DOSING IN RELATION TO CYCLE LENGTH**

Cycle Length (days)	Acceptable days for initiation of dosing		
21	Day 1 – Day 4	-or-	Day 11 to Day 21
22	Day 1 – Day 4	-or-	Day 12 to Day 22
23	Day 1 – Day 4	-or-	Day 13 to Day 23
24	Day 1 – Day 4	-or-	Day 14 to Day 24
25	Day 1 – Day 4	-or-	Day 15 to Day 25
26	Day 1 – Day 4	-or-	Day 16 to Day 26
27	Day 1 – Day 4	-or-	Day 17 to Day 27
28	Day 1 – Day 4	-or-	Day 18 to Day 28
29	Day 1 – Day 4	-or-	Day 19 to Day 29
30	Day 1 – Day 4	-or-	Day 20 to Day 30
31	Day 1 – Day 4	-or-	Day 21 to Day 31
32	Day 1 – Day 4	-or-	Day 22 to Day 32
33	Day 1 – Day 4	-or-	Day 23 to Day 33
34	Day 1 – Day 4	-or-	Day 24 to Day 34
35	Day 1 – Day 4	-or-	Day 25 to Day 35

Note: Subjects enrolled to the third oral dose (Treatment “D”) will have a dosing initiation visit scheduled 5-9 days before the anticipated start of their next menstrual cycle, based on their self-reported menstrual cycle length and the day the current menstrual cycle began.

## LIST OF ABBREVIATIONS

AE	Adverse event
AUC0-24	Area under the drug concentration versus time curve from 0 hour to 24 hours
AUC0-t	Area under the drug concentration versus time curve from 0 hour to t (time of the last observed non-zero concentration)
AUC0-inf	Area under the drug concentration versus time curve from 0 hour to infinity
bid	Twice daily
BLQ	Below the lower limit of quantitation
BMI	Body mass index
Cmax	Maximum concentration level
Css_oral	Steady state concentration level calculated for oral tablets
Css_im	Steady state concentration level calculated for IM injection
CSR	Clinical study report
Ct	The last observed non-zero concentration
CV	Coefficient of variation (equivalent to C.V.)
df	Degree of freedom
E2	Estradiol
ECG	Electrocardiogram
FDA	Food and Drug Administration
FSH	Follicle Stimulating Hormone
g	Gram
ICF	Informed consent form
IM	Intramuscular
Inc.	Incorporated
IV	Intravenous
Kel	The apparent elimination rate constant,
Kel Lower	The time point where K el calculation begins
Kel Upper	The sampling time of the last non-zero concentration used to estimate the K el
LH	Luteinizing Hormone
LMP	Last menstrual period
ln	Natural logarithm
Max	Maximum (equivalent to max.)
MedDRA®	Medical Dictionary for Regulatory Activities

---

mg	Milligram
Min	Minimum (equivalent to min.)
mL	Milliliter
n	Number of observations
No.	Number
PD	Pharmacodynamic; Postdosing
pH	Negative logarithm of the activity of H +
PK	Pharmacokinetic
PT	MedDRA ® Preferred Term
qd	Once a day
QRS	The QRS complex is a structure on the ECG that corresponds to the depolarization of the ventricles
QT	Time from electrocardiogram Q wave to the end of the T wave corresponding to electrical systole
QTcB	QT corrected with Bazett formula
QTcF	QT corrected with Fridericia formula
RR	Duration of ventricular cardiac cycle
SAE	Serious adverse event
SAP	Statistical analysis plan
SAS®	Statistical analysis system
SD	Standard deviation
SOC	MedDRA ® System Organ Class
SOP	Standard Operating Procedure
T1/2 el	Terminal elimination half-life
TEAE	Treatment-emergent adverse event
Tmax	Time to maximum concentration level
vs	Versus
WHO DD	World Health Organization Drug Dictionary

## 1. Introduction

This statistical analysis plan (SAP) is intended to give a detailed description of the summaries and the analyses that will be generated for the present study by inVentiv. Analyses specified in this plan are based on (and/or consistent with) Enteris BioPharma study protocol No. LOPDT-ENDO-01 Amendment 03 dated February 01, 2018 (inVentiv Project No. 160218). Safety, tolerability, pharmacokinetic (PK), and pharmacodynamics (PD) analyses will all be described.

The plan may be revised due to unforeseen circumstances and any changes or modifications made after the plan has been finalized will be documented. If additional or revised analyses are required to supplement the planned analyses described in the SAP, the changes and justification for the changes will be outlined in the clinical study report (CSR). No changes will be made without prior approval of the study sponsor. No formal justifications are required for changes to the SAP which do not affect the statistical analysis methods, definitions, or rules defined in this document.

When applicable, all analyses and related processes will be conducted according to inVentiv's Standard Operating Procedures (SOPs). Protocol deviations occurring during the study will be listed.

## 2. Study Objectives

The objectives are to determine the safety, PK profile, and PD effects of the three doses of Ovarest™ in healthy female volunteers in comparison to a marketed dose of leuprolide acetate administered intramuscular (IM) (Lupron Depot® 3.75 mg). Note: For the third Ovarest™ dose (Treatment "D"), a complete PK profile will not be evaluated.

This trial will serve as a bridging PK/PD study between the 4 mg Leuprolide Oral Tablet administered over 28 days as daily (qd) or twice daily (bid) regimens and the 10 mg Leuprolide Oral Tablet administered over 28 days as a bid regimen and a marketed IM injection of leuprolide acetate (Lupron Depot® 3.75 mg) designed for one month of therapy. This trial will also be a bridging study to historical PK/PD data for Lupron Depot® 3.75 mg and Lupron Depot® 11.25 mg (3-month) formulations.

The most important objective of this study is to provide adequate PD assessments to support development of the Leuprolide Oral Tablet with E2 suppression similar to those reported for Lupron Depot® and other E2-inhibiting hormonal therapies. Another reason for this trial is to describe the PK/PD dose-proportionality of the 4 mg and 10 mg Leuprolide Oral Tablet administered as qd and bid regimens.

## 2.1 Primary Objectives

- To determine the safety and to provide comparative evaluation of the PK and PD profiles of the 4 mg Leuprolide Oral Tablets in healthy, premenopausal female volunteers following qd and bid administration and the 10 mg Leuprolide Oral Tablets following bid administration in healthy, premenopausal female volunteers over 28 days vs a marketed formulation of leuprolide acetate administered IM for one month of therapy.
- To evaluate the PK properties of Leuprolide Oral Tablets after multiple dosing (i.e., 28 days of dosing)
- To assess the PK/PD dose-proportionality of the Leuprolide Oral Tablets administered as 4 mg qd, 4 mg bid and 10 mg bid dosing regimens
- To evaluate the PK and/or PD properties of the Leuprolide Oral Tablets (eg, E2 suppression rates) vs other hormonal therapies for the treatment of reproductive disorders, including endometriosis

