**Date**

4. PROTOCOL SYNOPSIS

Title of Study	A randomized, open-label, parallel-group, active-control study to evaluate the pharmacokinetic (PK) and pharmacodynamic (PD) profiles of three doses of Leuprolide Oral Tablets (Ovarest™) in comparison to an intramuscular (IM) dose of leuprolide acetate (Lupron Depot 3.75 mg) in healthy female volunteers
Protocol Number	LOPDT-ENDO-01
Phase	2a
Number of Study Centers	One or two sites, Phase I clinical unit(s) in the North America (US and/or Canada)
Investigational Product, Dosage, and Route of Administration	
Leuprolide Oral Tablets (Ovarest™) utilizing Enteris' Oral Peptide Delivery Technology. The Ovarest™ dosing regimens are selected based upon the results of the PK study LOPD-PH1-01.
 
The Ovarest™ dosing regimens are:  Treatment "A": Leuprolide Oral Tablet (Ovarest™), 4 mg, administered daily (qd) for 28 consecutive days  Treatment "B": Leuprolide Oral Tablet (Ovarest™), 4 mg, administered twice daily (bid), 12 hours apart for 28 consecutive days  Treatment "D": Leuprolide Oral Tablet (Ovarest™), 10 mg, administered twice daily (bid), 12 hours apart for 28 consecutive days

Control Drug (Reference Product)	Treatment C : Leuprolide Acetate intramuscular (IM) injection (Lupron Depot 3.75 mg) administered for one month of therapy
Study Design	Randomized, Open-Label, Parallel-Group, Active-Control Study for Treatment "A", Treatment "B" and "Treatment "C". Treatment "D" will be evaluated in a Non-Randomized, Open-Label, Single-Group Study design setting.
Study Objectives	
The objectives are to determine the safety, PK profile, and PD effects of the three doses of Ovarest™ in healthy female volunteers in comparison to a marketed dose of leuprolide acetate administered IM (Lupron Depot 3.75 mg). Note: For the third Ovarest dose (Treatment "D"), a complete PK profile will not be evaluated.
 
This trial will serve as a bridging PK/PD study between the 4 mg Leuprolide Oral Tablet administered over 28 days as qd or bid regimens, the 10 mg Leuprolide Oral Tablet administered over 28 days as a bid regimen, and a marketed IM injection of leuprolide acetate (Lupron Depot 3.75 mg) designed for one month of therapy. This trial will also be a bridging study to historical

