
Dose Justification of Treatment “D”
	
Pharmacodynamic data, specifically the suppression of estradiol, showed that both the 4 mg QD and BID regimens (Treatments “A” and “B”) fell substantially short of the suppression demonstrated by Lupron Depot®. Interim safety results from this study were also evaluated. Overall, Leuprolide Oral Tablets within a 4 mg to 8 mg daily dosing range were safe and reasonably well tolerated. The study results support a further dose increase in planned clinical evaluations.
 
Leuprolide Oral Tablets were shown to be safe and well tolerated in the Phase 1 study LOPDT-PH1-01, at doses of 1 and 4 mg in normal healthy volunteers. The absolute bioavailability was 2.2% and 3.0% for the 1 and 4 mg doses, respectively, compared to subcutaneous injection. The 4-mg Leuprolide Oral Tablet generated an overall drug exposure (a 24-hour AUC=19338 h*pg/mL) that was less than 12% of the drug exposure (163021 h*pg/mL) reported for a marketed 1-mg SC injection. A projected AUC for the 10 mg tablet administered twice daily (Treatment “D”) will be less than 60% of the 1-mg SC drug exposure. Projected Cmax of Treatment “D” will also be lower than Cmax reported for the 1-mg SC injection. These estimates clearly support the safety of the 10 mg tablet administered twice daily (Treatment “D”).
 
There is a further safety margin for the Treatment “D” dose of 10 mg bid: the Lupron Depot® 3.75 mg label contains the statement, “In early clinical trials using daily subcutaneous leuprolide acetate in patients with prostate cancer, doses as high as 20 mg/day for up to two years caused no adverse effects differing from those observed with the 1 mg/day dose.” Given the low bioavailability of the oral dose, about 3%, a substantial safety margin is assured.

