Leuprolide Oral Tablets were shown to be safe and well tolerated in the Phase 1 study LOPDT-PH1-01, at doses of 1 and 4 mg in normal healthy volunteers. The absolute bioavailability was 2.2% and 3.0% for the 1 and 4 mg doses, respectively, compared to subcutaneous injection. The 4-mg Leuprolide Oral Tablet generated an overall drug exposure (a 24-hour AUC=19338 h\*pg/mL) that was less than 12% of the drug exposure (163021 h\*pg/mL) reported for a marketed 1-mg SC injection. A projected AUC for the 10 mg tablet administered twice daily (Treatment “D”) will be less than 60% of the 1-mg SC drug exposure. Projected Cmax of Treatment “D” will also be lower than Cmax reported for the 1-mg SC injection. These estimates clearly support the safety of the 10 mg tablet administered twice daily (Treatment “D”).

Following the conclusion of LOPDT-PH1-01, Leuprolide Oral Tablets were reformulated in an effort to increase bioavailability. Reformulated tablets were administered to beagle dogs and the bioavailability was compared to the 4 mg dose from LOPDT-PH1-01. An increase in bioavailability was seen, from 2.2% for the Phase 1 tablet to 7.3% for the reformulated tablet. The reformulated 4 mg tablet (LEU-

012-17002) was then tested in this study, with 28 days of dosing in QD and BID regimens (Treatments “A” and “B”, respectively), and Lupron Depot 3.75 mg as an active comparator (Treatment “C”). Interim PK/PD results from this study were recently evaluated, which showed that the bioavailability of the reformulated tablet, rather than increase as predicted by testing in the dog, actually decreased to approximately 1.5%. Pharmacodynamic data, specifically the suppression of estradiol, showed that both the 4 mg QD and BID regimens fell substantially short of the suppression demonstrated by Lupron Depot®. Interim safety results from this study were also evaluated. Overall, Leuprolide Oral Tablets within a 4 mg to 8 mg daily dosing range were safe and reasonably well tolerated. The study results support a further dose increase in planned clinical evaluations.

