This protocol amendment include a fourth arm, which will be a 10 mg Leuprolide Oral Tablet administered BID for 28 days (Treatment “D”). As with the previous arms of the study, PD markers will be evaluated weekly during the 28 days of dosing and for a 28 day wash out period. The tablet formulation will revert to the more successful formulation used in the Phase 1 study, where the bioavailability was 3.0%. The amount of leuprolide projected to be absorbed into the circulation is 0.6 mg per day (3% of 20 mg). This is roughly equivalent to the 0.5 mg per day delivered by daily subcutaneous injection that was effective in treating uterine fibroids, and is approximately 60% of the 1 mg approved SC dose administered in the Phase 1 study. There is a further safety margin for the Treatment “D” dose of 10 mg bid: the Lupron Depot® 3.75 mg label contains the statement, “In early clinical trials using daily subcutaneous leuprolide acetate in patients with prostate cancer, doses as high as 20 mg/day for up to two years caused no adverse effects differing from those observed with the 1 mg/day dose.” Given the low bioavailability of the oral dose, about 3%, a substantial safety margin is assured.

The comparative PK/PD evaluations will form important bridges between different routes of leuprolide administration using both the company’s proprietary data and relevant published findings.

Additional information on Leuprolide Oral Tablet can be found in the Investigator's Brochure.

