### **7.1.1 Discussion of the Study Design**

With the weekly measurements of leuprolide and hormonal concentration levels, the study design is generally consistent with published PK/PD studies of Lupron Depot (Enteris BioPharma. Data on file).

Interim analysis of the PK portion of this study for Treatments “A” and “B” showed that the leuprolide exposure was approximately 6% and 12% of the exposure of a marketed 1 mg subcutaneous injection of

leuprolide. By returning to the formulation used in the phase 1 study (LOPDT-PH1-01), and by increasing the dose to 10 mg bid (Treatment “D”), the projected systemic exposure will be still less than 60% of the exposure of a marketed 1-mg subcutaneous injection of leuprolide. These estimates clearly support the safety of the 10 mg tablet administered twice daily (Treatment “D”). Further support for the safety of the 10 mg tablet administered twice daily is found in the Lupron Depot® 3.75 mg label, which contains the statement, “In early clinical trials using daily subcutaneous leuprolide acetate in patients with prostate cancer, doses as high as 20 mg/day for up to two years caused no adverse effects differing from those observed with the 1 mg/day dose.”

Additional information on PK properties of Leuprolide Oral Tablet can be found in the Investigator's Brochure.

The blood PK sampling schedule in this study for oral tablets is generally similar to that implemented in the study LOPDT-PH1-01. Since leuprolide oral tablets have a “peak-and-trough” PK pattern, their sampling schedule will be different from that of the Lupron Depot with its continuous drug release.

A once-weekly schedule of PD evaluations mimics a number of published E2 inhibition and ovulation suppression trials.

The following precautions are incorporated into the study to minimize bias:

- Subjects are sequentially assigned to randomly ordered treatment arm.
- Subject enrollment is dependent on satisfactory fulfillment of the inclusion/exclusion criteria with particular attention to contraindications to the leuprolide therapy as noted in (LUPRON DEPOT 3.75 mg, leuprolide for depot suspension. Full prescribing information).
- The person performing the PK/PD assays will be blinded to the oral treatment arms.

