## 10.3 Pharmacokinetic Concentration and Parameters

A total of 55 PK blood samples will be taken from subjects in the oral groups (Treatments “A” and “B”) for the evaluation of the leuprolide serum concentrations at Dosing period Day 1 and Day 28 immediately prior to dosing (0 time), and at 0.500, 1.00, 1.50, 2.00, 2.50, 3.00, 3.50, 4.00, 4.50, 5.00, 6.00, 7.00, 8.00, 10.0, 12.0, 13.0, 14.0, 15.0, 16.0, 17.0, 18.0, 20.0, and 24.0 hours following oral dosing and also in morning prior to dosing on Days 8, 15, and 22. There will be samples taken in Post-dosing Evaluation Period Day 7, 14, 21 and 28.

A total of 16 PK blood samples will be taken from subjects in the Lupron group (Treatment “C”) for the evaluation of the leuprolide serum concentrations at Dosing period Day 1 prior to dosing (0 time), at 0.500, 1.00, 2.00, 6.00, 12.0, 18.0, and 24.0 hours post-dosing, Day 8, 15, 22 and Post-dosing Evaluation Period Day 1, 7, 14, 21 and 28.

Subjects enrolled to the third oral dose (Treatment “D”) will have a very few PK samples: just prior to the first study drug administration and immediately prior to the first dose of the day on Treatment Days 8, 15, 22, and in the morning of Day 29. The PK samples will also be taken in Post-dosing Evaluation Period Day 7, 14, 21 and 28.

PK parameters will be calculated using the scheduled sample collection timepoints. For each evaluation period (*i.e.*: Treatment Days 1 and 28 for the oral groups and day 1 for the Lupron Depot group), where applicable, serum concentrations from leuprolide acetate will be used to calculate the following parameters by standard non-compartmental methods: Note: these PK parameters will be calculated for each treatment period for Treatment groups “A”, “B” and “C” only.

$AUC_{0-24}$  Area under the drug concentration versus time curve calculated using the linear trapezoidal method from 0 hours to 24 hours. In the case where the 24 hours concentration value is missing,  $AUC_{0-24}$  will not be calculated.

$AUC_{0-t}$  Area under the drug concentration versus time curve calculated using the linear

	trapezoidal method from 0 hours to t, where t is the time of the last available observation ( $C_t$ )
$AUC_{0-inf}$	Area under the drug concentration versus time curve from 0 hours to infinity, $AUC_{0-inf} = AUC_{0-t} + C_t/K_{el}$
$C_{max}$	Maximum concentration level

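### Treatment D changes formulation together with dose, so a D versus A/B difference cannot be read as dose-proportionality; SAP 11.2 also drops D from the concentration-PD display without listing this in Section 4

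*SAP*

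**What the plan says.** SAP 2.1 lists as a primary objective "To assess the PK/PD dose-proportionality of the Leuprolide Oral Tablets administered as 4 mg qd, 4 mg bid and 10 mg bid dosing regimens". SAP 2 states the purpose as "to describe the PK/PD dose-proportionality of the 4 mg and 10 mg Leuprolide Oral Tablet administered as qd and bid regimens". The protocol (Synopsis and Section 6) carries the same objective.

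Protocol Section 5 gives the tablet history. A and B received a 4 mg tablet reformulated after Phase 1, and its bioavailability in this study "actually decreased to approximately 1.5"%. For D, "The tablet formulation will revert to the more successful formulation used in the Phase 1 study, where the bioavailability was 3.0"%. Protocol 7.1.1 says of A and B that "the leuprolide exposure was approximately 6% and 12% of the exposure of a marketed 1 mg subcutaneous injection". The Synopsis projects that the AUC for D "will be less than 60% of the 1-mg SC drug exposure". The Synopsis also places D in a "Non-Randomized, Open-Label, Single-Group Study design setting", and Protocol 7.1 gives D its own window for starting treatment within the menstrual cycle.

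On PK, SAP 10.3 says "these PK parameters will be calculated for each treatment period for Treatment groups" A, B and C only. SAP 10.4 summarises D's concentrations by sampling time. SAP Table 3-1 describes A, B and D by strength and frequency and does not mention formulation.

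On concentration against response, the protocol (Synopsis, Statistical Methods; Section 12.3) plans correlations between leuprolide levels and PD parameters and excludes no arm. SAP 11.2 makes this a graphical examination and leaves D out without giving a reason. SAP Section 4, the stated place for changes from the protocol's planned analyses, has four items: the Day 29 timepoint, extra estradiol thresholds, suppression across intervals, and the adverse drug reaction analysis. The exclusion of D is not one of them.

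**The concern.** A dose-proportionality reading needs dose to be the factor that varies. Between A/B and D, tablet formulation varies too, and the documents' own figures suggest that its effect is not small. The SAP gives no dose-normalised summary and no rule for reading D against A and B, and its treatment table hides the difference. Someone working from the SAP tables could take a formulation effect for a more-than-proportional dose effect at 10 mg.

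The second part concerns the most direct evidence on whether more circulating drug goes with more suppression. D is the only oral arm above 8 mg per day. The oral arms left in the display are the two that Protocol Section 5 says fell well short of the depot on estradiol suppression. C remains, but as a depot injection. A planned analysis has therefore been narrowed, and the section meant to record such changes is silent.

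**Working it through.** **Inputs.** Bioavailability: about 1.5% for A/B and 3.0% for the Phase 1 formulation at 4 mg (2.2% at 1 mg). Phase 1 AUC: 19338 h·pg/mL for the 4 mg tablet against 163021 for 1 mg SC. Interim exposure relative to 1 mg SC: about 6% (A) and 12% (B). Daily doses: 4, 8 and 20 mg. All are in Protocol Sections 5 and 7.1.1 and the Synopsis.

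**Reproducing the plan's figures.** Absorbed amount = daily dose × bioavailability.
- A: 4 × 0.015 = 0.06 mg, or 6% of 1 mg SC. B: 8 × 0.015 = 0.12 mg, or 12%.
- D: 20 × 0.030 = 0.60 mg, as stated.
- By AUC: 19338/163021 = 11.9%, and 5 × 11.86% = 59.3%, consistent with the stated ceiling of 60%.

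**Projected exposure ratio against dose ratio.**

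| Contrast | Dose ratio | Exposure ratio (AUC basis) | Excess |
|---|---|---|---|
| D/B | 20/8 = 2.5 | 0.593/0.12 = 4.94 | 4.94/2.5 = 1.98 |
| D/A | 20/4 = 5.0 | 0.593/0.06 = 9.89 | 9.89/5 = 1.98 |
| B/A | 8/4 = 2.0 | 0.12/0.06 = 2.0 | 1.0 |

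The bioavailability basis gives 5.0 and 10.0, an excess of exactly 3.0/1.5 = 2.0. If D had the A/B bioavailability, it would absorb 20 × 0.015 = 0.30 mg. The ratios would then be 0.30/0.12 = 2.5 and 0.30/0.06 = 5.0, equal to the dose ratios. The whole projected excess therefore comes with the formulation.

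**How firm is the factor of 2?**
- Rounding of B (11.5% to 12.5%): excess 1.9 to 2.1. Rounding of A (5.5% to 6.5%): 0.593/0.065/5 = 1.8 to 0.593/0.055/5 = 2.2.
- Either reported Phase 1 bioavailability: 2.2/1.5 = 1.5 to 3.0/1.5 = 2.0.
- Assuming also that A/B bioavailability could be 1.3% to 1.7%: 2.2/1.7 = 1.3 to 3.0/1.3 = 2.3.
- The Phase 1 value rose between 1 mg and 4 mg, and 10 mg was not tested, so values outside these ranges cannot be excluded.

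**What the trial will provide for D.** D has 55 − 46 = 9 PK samples: Days 1, 8, 15, 22 and 29, and four follow-up visits. None supports an AUC. Under Protocol 7.2, leuprolide and hormones are both drawn shortly before the morning dose on Days 8, 15 and 22 (within 10 and 30 minutes respectively), and both in the morning of Day 29. With 12 subjects that is 12 × 3 = 36 pre-dose pairs plus 12 on Day 29, or up to 48 on-treatment pairs. I give no share of the whole display, because SAP 11.2 does not define which visits it uses.

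**Which values are comparable.** B and D are both dosed every 12 hours, so their pre-dose values on Days 8, 15 and 22 are nominal 12-hour troughs. A's are 24-hour troughs. With the label's half-life of about 3 hours (intravenous, healthy men; assumed to apply here), 12 hours is 4 half-lives, leaving 1/16 of the level, and 24 hours is 8, leaving 1/256. A's troughs therefore do not belong on the same footing.

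**The case against.** The strongest reply is that nothing planned would make the false attribution. SAP Section 8 plans no inferential analyses, and SAP 10.4 plans no formal between-treatment PK comparisons. The protocol discloses the formulation change, and D receives no AUC, Cmax or Css. The projected ratios of about 5 and 10 will therefore never appear in this trial's tables. This stands: error rates and power are untouched, and the ratios show only how large a formulation effect the sponsor's figures imply. It does not remove the point, because the objective still names 10 mg bid and the SAP carries no caveat.

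On the exclusion, both documents say that D will not have a complete PK profile, and the protocol leaves further PD detail to the SAP. That explains the missing AUC and Css. It does not explain leaving out paired single-time values, which the SAP otherwise summarises for D. A reader might infer that D was removed quietly or to shape the result. The documents do not support that: SAP 11.2 states the exclusion openly, and the gap is one missing entry in Section 4.

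A display with D may also show little. Levels 12 hours after a dose may be near or below the assay limit. No limit is given, and SAP 10.1 is unclear on how such values after Day 1 are plotted. D's home dosing times come from subject diaries. These are reasons for careful labelling, not for omission.

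**Conclusion.** The point holds as one of interpretation and documentation. D differs from A and B in formulation, dose, allocation and cycle-start window, so the D part of the dose-proportionality objective cannot isolate dose. The formulation factor implied by the protocol is about 2. It sets interim bioavailability from this study against a Phase 1 value at 4 mg, and the true factor at 10 mg is unknown.

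Two stronger readings are tempting and not supported. One is that the objective fails altogether. The three regimens can still be described, and A and B were randomized on the same tablet. The other is that A versus B can carry the dose-proportionality claim by itself. It compares one and two daily doses of the same 4 mg tablet, and on Day 28 the fasting window is −10 h to +4 h around A's dose and B's first dose but −2 h to +2 h around B's second (Protocol 7.2). It speaks to total daily dose, not to proportionality across tablet strengths.

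The exclusion of D is an unlisted change from the protocol. It leaves out up to 48 on-treatment pairs, assuming that 12 subjects enrol and complete those visits.

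**What to change.** 1. Delete the exclusion of D in SAP 11.2. Plot D's paired pre-dose values with B's for Days 8, 15 and 22, with D marked as a different formulation and non-randomized, and with values below the quantitation limit marked as such. Show Day 29 separately by time since last dose, noting that D's home dosing times are self-reported. If D is kept out, list and justify this in SAP Section 4.
2. State in the SAP, and list in Section 4, that D versus A/B is reported as a combined dose-and-formulation contrast and not as dose-proportionality. Describe A versus B (Day 28 AUC0-24) as proportionality to the total daily dose of one 4 mg tablet, with the fasting difference noted, and not as proportionality across strengths.
3. Add each arm's formulation to SAP Table 3-1.

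The cost is SAP text, one derived time variable and one extra plot, using samples already in the schedule. The downside is a narrower conclusion for this objective, and a D display limited to trough or morning levels, some of which may be below the quantitation limit.
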